## 5. INVESTIGATIONAL PRODUCT INFORMATION

Active zetomipzomib drug product or placebo will be provided. A prefilled syringe (PFS) containing diluent for zetomipzomib or placebo reconstitution may also be supplied as an investigational product (IP). Instructions for the receipt, inspection, storage, preparation, administration, and disposal of the IPs (including zetomipzomib or placebo and PFS) at clinical sites will be provided in a separate Pharmacy Manual.

# 5.1. Physical Description of Investigational Medicinal Product

Zetomipzomib or placebo is supplied as sterile lyophilized solids in single-use glass vials. Zetomipzomib or placebo is reconstituted with sterile water for injection (WFI) diluent prior to administration. Details of the formulation of zetomipzomib or placebo are provided in the Investigator's Brochure.

Placebo control will be reconstituted with sterile water for injection (WFI) diluent to an equivalent volume as the reconstituted zetomipzomib doses as per the Pharmacy Manual.

# 5.2. Diluent for Investigational Medicinal Product Reconstitution - Sterile Water for Injection

Commercially available sterile WFI formats may be used as diluent for zetomipzomib or placebo reconstitution. Alternatively, custom-manufactured and Sponsor-supplied PFS containing sterile WFI may be provided.

# 5.3. Ancillary Items

Ancillary items required for or used to facilitate the at-home reconstitution and administration of zetomipzomib or placebo such as vial adapters, alcohol wipes/swabs, syringes, and needles will be provided by a pharmacy, provided by the clinical site, supplied by the Sponsor, or prescribed by the Investigator.

# 5.4. Packaging and Labeling

Zetomipzomib or placebo will be packaged in cartons. PFS containing sterile WFI diluent will be packaged in pouches or cartons. All IP and ancillary items will be manufactured, packaged, and labeled according to Good Manufacturing Practice (GMP) and relevant regulatory requirements.

# 5.5. Supply, Dispensing, Storage, and Accountability

Refer to the most current version of the Pharmacy Manual for storage conditions of zetomipzomib or placebo. The current recommended storage condition for zetomipzomib or placebo is 2°C to 8°C. The current recommended storage condition for PFS is controlled room temperature.

Upon receipt of zetomipzomib or placebo, the Investigator (or designee) will conduct an inventory of the supplies and verify that they have been received in acceptable condition and in the correct amounts. The clinical site monitor (Monitor) may verify the study supplies at each study center at any time during the study.

The Investigator (or designee) must confirm that appropriate temperature conditions have been maintained during transit for all zetomipzomib or placebo received and that any discrepancies are reported to sponsor and resolved before their use.

Zetomipzomib or placebo should be stored in an environmentally controlled and monitored (manual or automated) area in accordance with the labeled storage conditions. Unless communicated as permissible by the Sponsor, excursions from labeled storage conditions must be reported to the Sponsor and resolved before use. Access to zetomipzomib or placebo must be limited to the Investigator and delegated authorized site personnel.

Only patients enrolled in the study may receive zetomipzomib or placebo.

The Investigator/Institution is responsible for the accurate and complete accountability and related record maintenance of zetomipzomib or placebo (eg, receipt, dispensing, use, reconciliation, and final disposition records). The Investigator/Institution may delegate some or all of the duties for zetomipzomib or placebo accountability to an appropriate pharmacist or another appropriate individual under the Investigator's supervision.

It is the responsibility of the Monitor to ensure that the Investigator (or designee) has correctly documented the amount of zetomipzomib or placebo received, dispensed, and returned/destroyed. Full IP accountability will be maintained by the site at all times. The Monitor will perform an inventory of zetomipzomib or placebo during the study and at the closeout visit to the site. All discrepancies must be accounted for and documented.

# 6. DOSAGE AND INVESTIGATIONAL MEDICINAL PRODUCT ADMINISTRATION

# 6.1. Zetomipzomib or Placebo Administration

Zetomipzomib or placebo will be administered by subcutaneous injection once weekly from Week 1 to Week 52 according to the Schedule of Assessments (Appendix 3). For all patients, the first and second doses of zetomipzomib or placebo will be administered at the clinical site. The first injection will be a 30-mg dose of zetomipzomib or placebo for all randomized patients. For patients randomized to 60 mg of zetomipzomib or placebo, the second and subsequent weekly injections will be at a 60-mg dose level of zetomipzomib or placebo. Patients randomized to 30 mg of zetomipzomib or placebo will continue to receive the 30 mg dose of zetomipzomib or placebo at all subsequent weekly injections.

After the second dose, zetomipzomib or placebo injections will either be administered by the patient/caregiver at home following training or via home health service at the patient's location, as appropriate, or by study personnel at the investigational site.

Proper handling, storing, reconstitution, administration, and disposal of zetomipzomib or placebo must be performed as described in the pharmacy manual or the Instructions for Use (IFU).

Patients/caregivers will be provided with the IFU to ensure proper handling, storage, reconstitution, administration, and disposal of zetomipzomib or placebo and ancillary items dispensed.

#### **6.1.1.** Administration Site

Subcutaneous injection sites should be rotated (eg, 4 abdominal quadrants, posterior upper arms, and anterior thighs), and a minimum of 4 weeks should separate injections to the same anatomic site, if possible.

# 6.1.2. Suggested Measures to Improve Tolerance to Systemic Injection Reactions (SIRs)

Initial subcutaneous doses of zetomipzomib are occasionally associated with at least 1 of the following signs/symptoms regarded as SIRs: hypotension, tachycardia, nausea, vomiting, dizziness, headache, pyrexia, rigors, and/or chills. The events are associated with an acute phase-like response, including leukocytosis and elevated C-reactive protein, typically begin within 8 to 24 hours after dosing, and usually resolve within 48 hours of dosing.

Although the numbers are small, the percentage of patients reporting TEAEs of the above signs/symptoms appears to be lower in patients who received zetomipzomib as step-up doses and/or with pre/post dose prophylaxis, suggesting that these methods are effective at tolerizing patients to higher doses of zetomipzomib.

# Step-up dosing

All patients randomized to 60 mg in this study will receive an initial dose of 30 mg to be followed weekly by the target dose of 60 mg.

## Pre/Post dose prophylaxis

Prophylactic measures may be considered if any of the aforementioned signs and/or symptoms develop and may be used as treatment, either while the patient is at the study site or after the patient leaves the study site. Measures that have been demonstrated to reduce the incidence and severity of infusion-related reactions with other proteasome inhibitors include the following:

- fluid hydration is strongly encouraged, eg, 250 to 500 mL oral (or IV, if necessary) of an electrolyte solution up to 48 hours prior to dosing or up to 24 hours after dosing (if symptoms are present)
- antiemetics, nonsedating antihistamines, and/or acetaminophen

If additional guidance for improving initial tolerability symptoms is required, the Medical Monitor should be consulted. Home health service staff do not provide or administer any of the fluids or medications listed above.

#### 6.1.3. Dose Modification Guidelines

#### 6.1.3.1. Dose Reduction

Patients who experience a treatment-related AE at the 60-mg dose of zetomipzomib or placebo will be permitted to undergo dose reduction to the 30-mg dose of zetomipzomib or placebo for subsequent doses at the discretion of the Investigator, in consultation with the Medical Monitor. Patients on the 30-mg dose are not able to have a dose reduction. Approval from the Medical Monitor should be obtained in advance of implementing dose reduction, when possible. After dose reduction is implemented, patients should remain on the reduced dose for at least 2 doses, after which re-escalation to the patient's originally assigned dose should be attempted/encouraged. If the original dose is not tolerated after re-escalation, a reduced dose may be continued for the remainder of the study at a minimum 30-mg dose of zetomipzomib or placebo, or re-escalation may be reattempted after written approval from the Medical Monitor. Any dose modifications should be documented in the electronic case report form (eCRF) as per Section 9.1.4.

## 6.1.3.2. Missed Doses

Doses should be administered within the visit windows as per the Schedule of Assessments (Appendix 3). Any doses administered outside the visit window will be considered a protocol deviation; however, if necessary to avoid missing a dose, doses may be administered up to 3 days from the date of the scheduled administration with a minimum of 4 days required between doses.

Patients who meet individual patient stopping rules (Section 8.1.2) may resume administration of zetomipzomib or placebo after discussion between the Investigator and Medical Monitor. Upon resumption of dosing, subsequent doses should be timed according to the original dosing schedule based on Day 1 (Week 1). Patients who are discontinued for missed doses should have their discontinuation recorded in the eCRF based on the reason the doses were missed (eg, AE or protocol non-compliance). The Investigator should contact the Medical Monitor if a patient missed >3 consecutive doses or >7 total doses to determine if the patient should resume administration of zetomipzomib or placebo.

If zetomipzomib or placebo is permanently discontinued due to an AE, the planned assessments (Appendix 3) should continue for the protocol-specified time period. If the patient cannot continue with the planned assessments, the ETV and the 4-week safety follow-up (EOS) visit should be accomplished at a minimum.

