## 8.1.2. Individual Patient Stopping Rules

The Investigator and Sponsor may discontinue the patient from zetomipzomib or placebo administration or study participation at any time if discontinuation would be in the patient's best interest. In the event that zetomipzomib or placebo is discontinued, the patient should be encouraged, where possible, to remain in the study.

Reasons for discontinuing a patient from zetomipzomib or placebo administration include, but are not necessarily limited to, any one of the criteria listed below.

- Receipt of a kidney transplant or initiation of dialysis
- Grade 4 (life-threatening) TEAE, unless due to an obvious alternative etiology
- Confirmed thrombotic microangiopathy (TMA)
- Serious allergic reaction to zetomipzomib or placebo, including anaphylaxis
- HIV/acquired immune deficiency syndrome or viral hepatitis (B or C) infection occurring during the study
- Pregnancy

- Any medical condition or personal circumstance that, in the opinion of the Investigator, exposes the patient to risk if the patient continues with zetomipzomib or placebo or that prevents the patient's adherence to the protocol
- Protocol deviation involving inclusion or exclusion criteria or concomitant medications (Section 6.2) that, in the Investigator or the Sponsor's judgment, would significantly compromise data interpretation or patient safety

The Investigator must contact the Medical Monitor to discuss further continuation if after 12 weeks of treatment, at 2 consecutive visits at least 4 weeks apart, either of the following criteria is met:

- UPCR does not decrease >25% from the last Screening result
- eGFR <60 mL/min/m² and decreases of >20% from the last Screening result Note: If the patient is not discontinued, and UPCR or eGFR thresholds are subsequently met but remain stable in the judgment of the Investigator and Medical Monitor, then the Investigator must also contact the Medical Monitor to discuss further continuation at least every 12 weeks.

Furthermore, zetomipzomib or placebo should be interrupted, and the patient should be evaluated if there is a suspected diagnosis of thrombotic microangiopathy, such as with any acute changes in renal function, thrombocytopenia, or intravascular hemolytic anemia.

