## 9.5.2. Thrombotic Microangiopathy

Cases of thrombotic microangiopathy, including thrombocytopenic purpura and hemolytic uremic syndrome, have been described with the proteasome inhibitors, bortezomib, carfilzomib, and ixazomib. The clinical presentation of thrombotic microangiopathy typically includes fever, microangiopathic hemolytic anemia (with schistocytes on blood smear), thrombocytopenia, renal failure, purpura, and neurological manifestations. Patients should be monitored for signs and

symptoms of thrombocytopenic purpura/hemolytic uremic syndrome. If the diagnosis is suspected, such as with any acute changes in renal function, thrombocytopenia or intravascular hemolytic anemia, interrupt zetomipzomib or placebo administration and evaluate (refer to Section 8.1.2). Missed doses should be addressed as per Section 6.1.3.2. If the diagnosis of thrombocytopenic purpura/hemolytic uremic syndrome is excluded, zetomipzomib or placebo may be resumed. If the diagnosis is confirmed, zetomipzomib or placebo must be permanently discontinued (refer to Section 8.1.2).

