## 9.7. Hypersensitivity Reactions

Hypersensitivity reactions are exaggerated or inappropriate immunologic responses occurring in response to an antigen or allergen. Drugs may cause allergic reactions by any mechanism of hypersensitivity. For example, penicillin may cause anaphylaxis, which is IgE-mediated, but most responses are trivial. Hypersensitivity reactions to zetomipzomib are not anticipated given its structure and mechanism of action; however, potential hypersensitivity to an excipient could occur. Studies in compound ONX 0914, an analog of zetomipzomib, demonstrated inhibition of T-helper 2 cell response and allergic reactions in foreign ovalbumin and house dust mite induced allergic airway inflammation in mouse models.

Known risk factors for developing a hypersensitivity reaction include allergic reaction history, concomitant diseases such as chronic respiratory diseases, cardiovascular diseases, mastocytosis or clonal mast cell disorders, and severe atopic disease. Some concurrent medications such as beta-adrenergic blockers and ACE inhibitors might also increase the risk. Patients in this study should be closely monitored. Should any signs and symptoms of suspected hypersensitivity reactions occur, the Investigator will diagnose per clinical guideline and zetomipzomib or placebo may be temporarily withheld. If the diagnosis of hypersensitivity is confirmed, zetomipzomib or placebo must be permanently discontinued, and the patient will be treated per clinical guidelines.

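### Protocol 6.1.3.2 lets a patient who meets any Section 8.1.2 stopping rule resume study drug, while 9.5.2 and 9.7 require permanent discontinuation after confirmed TMA or hypersensitivity

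*Protocol*

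**What the plan says.** The rule on resuming is in Protocol Section 6.1.3.2 (Missed Doses): "Patients who meet individual patient stopping rules (Section 8.1.2) may resume administration of zetomipzomib or placebo after discussion between the Investigator and Medical Monitor". SAP Section 3.4.2 carries the same sentence.

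Section 8.1.2 gives eight bulleted reasons for stopping study drug. Two of them are "Confirmed thrombotic microangiopathy (TMA)" and "Serious allergic reaction to zetomipzomib or placebo, including anaphylaxis". A separate paragraph of that section deals with suspicion rather than confirmation: "zetomipzomib or placebo should be interrupted, and the patient should be evaluated if there is a suspected diagnosis of thrombotic microangiopathy". Nothing in Section 8.1.2 marks any bullet as permanent.

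The event-specific sections are stricter.

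- Section 9.5.2, on suspected TMA: "Missed doses should be addressed as per Section 6.1.3.2". It then separates the two outcomes: "If the diagnosis of thrombocytopenic purpura/hemolytic uremic syndrome is excluded, zetomipzomib or placebo may be resumed", but "If the diagnosis is confirmed, zetomipzomib or placebo must be permanently discontinued (refer to Section 8.1.2)".
- Section 9.7, on allergic reactions: "If the diagnosis of hypersensitivity is confirmed, zetomipzomib or placebo must be permanently discontinued".

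**The concern.** The dosing section and the safety sections answer the same question differently. After confirmed TMA or a confirmed serious allergic reaction, Section 6.1.3.2 leaves resumption open to the Investigator and Medical Monitor, whereas Sections 9.5.2 and 9.7 leave no discretion.

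What is at stake is patient safety. Section 9.5 makes TMA an adverse event of special interest. Section 9.5.2 notes cases with bortezomib, carfilzomib and ixazomib, and Section 1.2 describes zetomipzomib as structurally similar to carfilzomib. After the second dose, injections may be given at home (Section 6.1), and Section 6.1.3.2 does not require a resumed dose to be given on site. Site staff and the Medical Monitor need a single rule for these two events.

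**Working it through.** No formula applies, since the point depends on no sample size, power, alpha or event rate. The check is a comparison of the texts.

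**Scope of the resume sentence.** It covers patients who meet the Section 8.1.2 rules. Its one condition is a discussion, and it excludes no rule.

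**Count of the Section 8.1.2 bullets.** (1) kidney transplant or dialysis; (2) Grade 4 event; (3) confirmed TMA; (4) serious allergic reaction; (5) HIV or viral hepatitis; (6) pregnancy; (7) medical condition or personal circumstance; (8) protocol deviation. Two of the eight, (3) and (4), are subject elsewhere to an explicit requirement that discontinuation be permanent.

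**Side by side.**

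| Event | Section 8.1.2 | Section 6.1.3.2 and SAP 3.4.2 | Event-specific section |
|---|---|---|---|
| Suspected TMA, later excluded | Interrupt and evaluate | May resume | 9.5.2: may resume |
| Confirmed TMA | Stopping criterion | May resume | 9.5.2: permanent stop |
| Serious allergic reaction, confirmed as hypersensitivity | Stopping criterion | May resume | 9.7: permanent stop |

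The first row is consistent; the second and third are not. The match is exact for TMA. For Section 9.7 it runs through serious reactions, because Section 8.1.2 does not name non-serious hypersensitivity, although its list is stated to be non-exhaustive.

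**Where the cross-references lead.** Section 9.5.2 cites Section 8.1.2 in support of the permanent stop, but 8.1.2 does not say permanent. Section 6.1.3.2 then says that patients who meet 8.1.2 may resume. Section 9.5.2 also points directly to 6.1.3.2 for missed doses. A reader who follows either reference from the TMA section can arrive at the unrestricted permission.

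**Link to the analysis.** Discontinuation of study drug is a treatment-failure criterion (Protocol 2.2.5; SAP Table 4), and SAP 8.2.2 counts a patient with such an event before Week 37 as a non-responder. Whether one of these patients stays off drug or resumes could therefore affect that patient's classification.

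**The case against.** The strongest reply is that the texts can be followed together. Section 6.1.3.2 only permits resumption, and only after a discussion; it directs no one to re-dose. Sections 9.5.2 and 9.7 are mandatory and specific to the event, so the discussion would end in no resumption. Context supports this reading. Section 6.1.3.2 is about missed doses, and its third paragraph treats permanent discontinuation for an adverse event as a separate outcome. In Section 9.5.2 the reference to 6.1.3.2 comes before the excluded and confirmed branches, so it most naturally concerns doses missed during work-up, and the two deciding sentences follow at once. Section 9.7 contains no reference to 6.1.3.2, and its trigger only overlaps with the bullet in 8.1.2. The SAP sentence restates protocol text and does not govern dosing at sites.

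Much of this stands. It is probably how a careful reader would resolve the conflict, the hypersensitivity half is the looser match, and the SAP edit is for consistency only. A resume route is also sensible for suspected TMA that is later excluded and for the judgement-based criteria.

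It does not remove the problem. No section says that the specific rule prevails. Section 6.1.3.2 speaks of stopping rules, not interruptions, although Section 8.1.2 keeps the two apart. The discussion is a real safeguard, but a lighter one than Section 6.1.3.1 asks for when re-escalation is tried again after the original dose was not tolerated, where written approval is needed. With about 250 sites planned in Protocol 3.3 (about 214 in SAP 4.2), a safety rule should not depend on how each reader reconciles two sections.

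**Conclusion.** The concern holds. As written, the dosing section permits study drug to be restarted after confirmed TMA or anaphylaxis, and the safety sections forbid it. The conflict is confined to 2 of the 8 bulleted criteria in Section 8.1.2. How many patients it would touch cannot be calculated, because neither document gives a rate for either event; few is the reasonable expectation, given that Section 9.7 does not anticipate hypersensitivity reactions. Any effect on responder classification would concern equally few. Sample size, power and alpha are unaffected.

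The conclusion takes Section 6.1.3.2 at its literal meaning and assumes that Sections 9.5.2 and 9.7 state the sponsor's actual intention. The change should be made, on grounds of patient safety and consistency.

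**What to change.** Open the resume sentence in Protocol Section 6.1.3.2 with an exception, for example:

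> Except after confirmed TMA, including TTP/HUS (Section 9.5.2), or confirmed hypersensitivity, including serious allergic reaction or anaphylaxis (Section 9.7), for which study drug is stopped permanently, patients who meet …

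Put the same clause in SAP Section 3.4.2, with the section numbers identified as the protocol's. In Protocol Section 8.1.2, mark the TMA and serious-allergic-reaction bullets as permanent. The sponsor should decide whether any of the other six bullets also warrants that mark.

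The cost is one clause in each document and a mark on two bullets. It introduces no new policy, since it aligns the dosing text with what Sections 9.5.2 and 9.7 already require, and it keeps the resume route for the cases where that route makes sense. Design, analysis and sample size do not change.

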# **6.2.** Prior and Concomitant Medications

A concomitant medication is any prescription or over-the-counter preparation, including vitamins and supplements. Any concomitant medications must be recorded on the eCRF. Except as described below, prior and concomitant medication use will be recorded for the 60 days prior to Screening until the patient's last follow-up visit.

All prior systemic SLE treatment (eg, immunosuppressive agents, antimalarials, and biologics) will be recorded, including corticosteroid use and any topical use from at least the previous 24 weeks prior to Screening. When possible, all prior CYC, MMF, IV methylprednisolone, calcineurin inhibitors (eg voclosporin and tacrolimus), and biologics (eg, belimumab and rituximab) should be recorded. Details to be recorded include, but are not limited to, the concomitant medication generic name, dose, route, frequency of administration, and indication.

Patients should remain stable on their medications during the treatment period, as outlined in the inclusion/exclusion criteria (Sections 4.2 and 4.3) and in this section.

